#### 6.4.3 CRITERIA FOR NONLOCAL FAILURE (Secondary Objectives)

If clinically indicated, a bone scan, CT or other imaging study may be performed to assess distant failure. This is conventional care and would be done if the treating physicians feels it is necessary.

##### 6.4.3.1 **DISTANT FAILURE** (includes regional failure)

documented if clinical, bone scan, CT or other imaging study shows metastatic disease. Biochemical failure with a negative prostate biopsy shall be considered distant only failure. Biopsy of metastatic site required if radiographic or clinical findings are equivocal. Type of metastatic failure (distant and/or regional) shall be recorded if known.

Prostate biopsy recommended at this time.

##### 6.4.3.2 **DISEASE-FREE SURVIVAL**: for any measure of disease, including PE, PSA, bone scan, CT/MRI and biopsy, or death.

##### 6.4.3.3 **DISEASE-SPECIFIC SURVIVAL**: for any of the following:

6.4.3.3.1 Death due to prostate cancer.

6.4.3.3.2 Death due to other causes, with active malignancy (defined by clinical or biochemical evidence of progression). If a patient suffered a previous relapse, but has inactive disease, this is not considered a disease-specific death.

6.4.3.3.3 Death due to complications of treatment.

6.4.3.3.4 **OVERALL SURVIVAL**: for death from any cause

## 7.0 Statistical Considerations

7.1 **OVERVIEW**: This study’s primary goal is to determine the **rate** of acute and late grade 3-5 gastrointestinal and genitourinary toxicity following SBRT treatment, and to estimate efficacy, measured as 2-year bDFS. Per RTOG/ECOG, acute toxicity will be defined as occurring within 90 days of completing treatment. Late toxicity will be defined as toxicity occurring more than 90 days after treatment. It is graded based on Common Terminology Criteria for Adverse Events (CTCAE) v3.0.(see section 8.0)

## 7.2 SAMPLE SIZE:

7.2.1 PRIMARY SAFETY OBJECTIVE: The study is designed to test the null hypothesis that the acute and late GI/GU toxicity rate 2 years following treatment is less than 10% versus the alternative hypothesis that the toxicity rate is greater than or equal to 10%. If we end up with 200 eligible patients, there will be 99% probability, or statistical power, of identifying excessive toxicity if the true

toxicity rate is 20%, at the one-sided significance level ( $\alpha$ ) 0.05. The intervention will be considered to be safe if the acute and late GI/GU toxicity rate 2 years following treatment is not above 10%

7.2.2 PRIMARY EFFICACY OBJECTIVE: The study is powered to compare 2-year bDFS rates observed with SBRT to 2-year bDFS rates reported with dose-escalated external beam RT. In Beaumont's monotherapy HDR series treating patients, 5-yr ASTRO bDFS was 97.5%; in Demanes' series of 75% LR and 25% IR, this was 96%. We would expect Phoenix outcomes to be slightly higher than ASTRO outcomes at 5 years. Since SBRT delivers doses similar to HDR monotherapy, a conservative estimate of the success rate for SBRT is 97.5%. In LR patients, prospective studies from Memorial Sloan Kettering (203 patients, 81Gy) and MD Anderson (32 patients, 78Gy) demonstrated 5-yr bDFS (Phoenix definition) of 92% and 92%, respectively. Thames' 9-institution review of 231 dose-escalated (70-76Gy) LR patients reported 94% 5-yr Phoenix bDFS. Thus, an objective performance criteria (OPC) for low-risk patients treated with dose-escalated external beam RT is 92% 5-yr bDFS. If we assume the SBRT success rate is 97%, a sample size of 200 patients will provide 99% power to test superiority of SBRT against this OPC with 80% power at the 1-sided 5% significance level. If we assume the SBRT success rate is 96%, then the power will be 78%.

7.2.3 TOTAL AND RELATIVE ENROLLMENT: Per above sections 7.2.1-7.2.2, we plan to accrue 200 eligible patients to compare the 2-year bDFS rate observed with SBRT to the 2-year OPC rate, and to establish acceptable toxicity. The test cohort will be closed to accrual once requisite enrollment is achieved: 200 total patients.

7.2.4 ACCRUAL RATE: The accrual rate will be 5–6 patients / month over 2 years.

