## 7.3 STATISITCAL METHODS:

The *primary* objectives of this study are:

- To determine, in both low-risk and intermediate-risk cohorts, the rates of acute and late grade 3 or higher gastrointestinal and genitourinary toxicity observed during an initial 24 month follow up.
- To estimate the rate of biochemical Disease-Free Survival (bDFS), Phoenix and ASTRO definitions, at 2 years following hypofractionated SBRT for low and intermediate risk prostate cancer. Failure occurs when the PSA is  $\geq 2$  ng/ml more than the lowest PSA measurement before the current one, with no backdating.

The *secondary* objectives of this study are to:

- the rate of local failure: proportion of patients with local disease progression at 2 years

- rate of distant failure: proportion of patients with metastatic disease at 2 years
- rate of disease-free survival: median time from start of treatment until disease progression
- rate of disease-specific survival: death due to prostate cancer (excludes patients that relapse with inactive disease)
- overall survival: median length of time from either the date of diagnosis or the start of treatment for a disease, such as cancer, that patients diagnosed with the disease are still alive.
- quality of life (QOL) in generic and organ-specific domains using the FACT-G assessment tool

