### 7.3.1 PRIMARY ENDPOINTS:

Wilson score interval is used to determine the confidence intervals for the expected proportion of patients experiencing a “success” outcome.

7.3.1.1 SAFETY: The upper limit of a one-sided 95% confidence interval for the expected proportion of patients experiencing any grade 3-5 acute or late toxicity as defined above in 7.1, is estimated by U, where

$$U = \frac{(2np + Z_{0.95}^2) + Z_{0.95} \sqrt{Z_{0.95}^2 + 4np(1-p)}}{2(n + Z_{0.95}^2)}$$

where:

p: the observed proportion of patients experiencing any grade 3-5 acute or late toxicity as defined above in 7.1;  
n: the total number of patients;  
 $Z_{0.95} = 1.645$ .

The intervention will be considered to be safe if this study’s result verifies that U is not above 10%i.

7.3.1.2 EFFICACY: The lower limit of a one-sided 95% confidence interval for the expected proportion of patients experiencing biochemical disease-free survival (bDFS) is estimated by L, where

$$L = \frac{(2np + Z_{0.95}^2) - Z_{0.95} \sqrt{Z_{0.95}^2 + 4np(1-p)}}{2(n + Z_{0.95}^2)}$$

where:

p: the observed proportion of patients experiencing bDFS;  
n: the total number of patients;  
 $Z_{0.95} = 1.645$ .

The SBRT intervention will be considered to be effective if this study’s result verifies that L is not below 92%.

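### The pass mark for 2-year bDFS in all patients is a 5-year, low-risk external-beam rate (92%), so the one-sided 5% level is not assured against a like-for-like 2-year comparator

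*Combined protocol and SAP*

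**What the plan says.** **The comparison promised.** Section 7.2.2 opens: "The study is powered to compare 2-year bDFS rates observed with SBRT to 2-year bDFS rates reported with dose-escalated external beam RT". Section 7.2.3 gives the purpose of enrolling 200 patients as "to compare the 2-year bDFS rate observed with SBRT to the 2-year OPC rate".

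**The benchmark derived.** Section 7.2.2 cites three external-beam results: 92%, 92% and a nine-institution review that "reported 94% 5-yr Phoenix bDFS". All three are 5-year Phoenix rates in low-risk men. It concludes: "Thus, an objective performance criteria (OPC) for low-risk patients treated with dose-escalated external beam RT is 92% 5-yr bDFS". Table 1 is likewise titled low-risk and headed 5-year bDFS.

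**The endpoint and population.** Section 7.1 sets the aim "to estimate efficacy, measured as 2-year bDFS". Section 7.3 describes bDFS "at 2 years following hypofractionated SBRT for low and intermediate risk prostate cancer". Section 4.3 admits intermediate-risk men and states no planned share.

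**The decision rule.** Under 7.3.1.2, SBRT counts as effective if the study's "result verifies that L is not below 92" per cent. L is the one-sided 95% Wilson lower limit, with "n: the total number of patients".

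**The assumed SBRT rates.** The 97% and 96% used for power in 7.2.2 carry no time label. They follow 5-year HDR results.

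**The concern.** The benchmark differs from the quantity tested in two ways: time (5 years against 2) and risk group (low only against low plus intermediate). Nothing in the documents converts 92% to 2 years, supplies an intermediate-risk external-beam rate, or confines the efficacy test to low-risk men.

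This matters because 7.3.1.2 is the only decision rule for the primary efficacy objective. Section 7.2.2 presents the comparison as a superiority test at the one-sided 5% level. If 92% is not the rate that external beam would achieve at 2 years in the enrolled mix, passing the rule does not show what 7.2.2 and 7.2.3 say it shows.

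**Working it through.** **Inputs.** n = 200, z = 1.645, threshold 92%, assumed SBRT rates 97% and 96% (7.2.2, 7.3.1.2). All calculations take 2-year status as known for all 200 men.

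**1. The rule.** With p = x/n, L = [(2np + z²) − z√(z² + 4np(1 − p))] / [2(n + z²)].
- x = 190: L = 91.81%, fails.
- x = 191: L = 92.42%, passes.

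So the rule is at least 191 of 200.

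**2. The plan's own figures.** The exact error, P(X ≥ 191), at a true 92% is 3.7%. Exact power is 91.9% at 97% and 71.9% at 96%. The plan states 99% (and, in the same sentence, 80%) at 97%, and 78% at 96%. No single method tried gives both 99% and 78%; that is a separate matter. What counts here is that the power statement takes 92% as its null, so the 5-year low-risk figure sits behind the power as well as the pass mark.

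**3. Error against a matched comparator.** If SBRT exactly equals the true 2-year external-beam rate in the enrolled mix, the chance of passing is:

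| Matched 2-year rate | P(191 or more of 200) |
|---|---|
| 91% | 1.2% |
| 92% | 3.7% |
| 93% | 10.1% |
| 94% | 23.4% |
| 95% | 45.5% |
| 96% | 71.9% |

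The error crosses 5% at about 92.3%.

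**4. Time mismatch alone.** Under the Phoenix definition behind the benchmark, a failure is not reversed. The 2-year rate therefore cannot be below the 5-year rate and is probably above it. This ordering is claimed for Phoenix only: 6.4.1.2 cancels some early ASTRO failures when PSA later declines. Assume all 200 men are low-risk and a Weibull shape k (constant hazard is k = 1). Then S(2) = 0.92^(0.4^k).

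| k | 2-year rate | An equal regimen passes |
|---|---|---|
| 0.5 | 94.9% | 42% |
| 1 | 96.7% | 87.6% |
| 1.5 | 97.9% | 99% |

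**5. Adding the risk mix.** The documents give neither an intermediate-risk external-beam rate nor a share, so both are assumed. The low-risk 5-year rate stays at 92% and the hazard is constant in each group.
- 25% intermediate-risk with a 5-year rate of 90%: matched 2-year rate 96.5%; an equal regimen passes 84% of the time.
- 50% with 80%: 94.1%; passes 25%.
- 75% with 70%: 89.2%; passes 0.1%.

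The result runs from well above 5% to well below it. Only an assumption about the mix and the intermediate-risk rate decides which.

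**The case against.** **The 5% level is met as worded.** Section 7.2.2 claims superiority against the OPC, and against the number 92% the exact error is 3.7%. That is correct. But 7.2.2 and 7.2.3 also say that the OPC stands for a 2-year external-beam rate, and that link is missing.

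**The risk-mix half is a design criticism, not a textual contradiction.** This also stands in part. The 2-year against 5-year clash is in the plan's own words. That intermediate-risk men have lower external-beam bDFS is plausible, but no external-beam figure in the documents shows it. The mixed-risk series cited (75% low, 25% intermediate) is HDR.

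**The objective is to estimate.** Sections 7.1 and 7.3 do speak of estimating 2-year bDFS, and that estimate is untouched. Section 7.3.1.2 nevertheless adds a pass/fail verdict.

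**A stronger reading to avoid.** A reader might infer that the bar is simply too lenient and the type I error inflated. The documents do not support that. The time mismatch probably makes 92% too low for low-risk men, but its size rests on an assumed hazard shape, and the risk mix may offset or reverse it.

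**Conclusion.** The concern holds as a mismatch between the benchmark promised and the one used. A 2-year external-beam comparator is announced, only a 5-year low-risk one is derived, and it becomes the pass mark for a 2-year endpoint in all patients. The one-sided 5% level holds against the number 92% (3.7%) but is not assured against a like-for-like comparator; it is exceeded once that comparator is above about 92.3%.

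The 87.6% pass rate for an equal regimen rests on two assumptions: all men low-risk and a constant hazard. The range is 42% to 99% for shapes 0.5 to 1.5. With intermediate-risk men included, the net direction cannot be determined from the documents.

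Nor should a reader infer that the primary efficacy result as a whole is invalid. The 2-year bDFS estimate and its interval stay valid; only the effectiveness verdict and the superiority claim are affected. Because that verdict is the sole primary efficacy rule, it must be fixed.

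**What to change.** **First choice.** In 7.2.2, 7.2.3 and 7.3.1.2, replace 92% with a sourced 2-year external-beam benchmark, given by risk group or weighted to the enrolled mix. Name the bDFS definition that is tested. Re-derive the assumed SBRT rates as 2-year rates rather than relabelling figures that rest on 5-year HDR data. Restate the power.

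*Cost.* No added visits, but possibly a large loss of power. For an all-low-risk bar of 96.7% (constant hazard), the same Wilson rule needs 198 of 200. If 97% is a 5-year SBRT rate, it becomes 0.97^0.4 = 98.8% at 2 years and power is 56%. If 97% is the true 2-year rate, power is 5.9%. So 200 patients may not support a superiority test.

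**If no such benchmark can be sourced, or power is inadequate.** Report 2-year bDFS with its interval, and delete the effectiveness verdict and the superiority statement against 92%.

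*Optional new analysis.* Compare 5-year Kaplan-Meier Phoenix bDFS in low-risk men with 92%. The plan has no such analysis now: 7.3.2.3 lists Kaplan-Meier only for disease-free, disease-specific and overall survival. With an assumed 100 or 150 low-risk men and no censoring, 97 of 100 or 144 of 150 are needed, and power at a true 97% is 65% or 83%. This depends on 5-year PSA follow-up being confirmed. Section 2.1 and note b in section 6.0 should be checked against each other on that point; the schedule table was not readable here, so which assessments note b governs could not be seen.

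### Section 7.2.2 gives two powers (99% and 80%) for one efficacy test; under the plan's own rule 200 men give 91.9% at a true rate of 97%, and 71.9%, not 78%, at 96%

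*Combined protocol and SAP*

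**What the plan says.** Section 7.2.2 takes 92% as the objective performance criterion (OPC) and makes two power statements, both for 200 patients at the one-sided 5% level.

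- At a true rate of 97%: "a sample size of 200 patients will provide 99% power to test superiority of SBRT against this OPC with 80% power".
- "If we assume the SBRT success rate is 96%, then the power will be 78"%.

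Earlier in the same paragraph a different planning value appears: "a conservative estimate of the success rate for SBRT is 97.5"%.

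Section 7.3.1.2 defines the test. It computes a one-sided 95% Wilson lower limit L with Z = 1.645, and SBRT is effective if the "result verifies that L is not below 92"%. The plan gives no other efficacy test and no power formula.

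On enrollment, section 7.2.3 says the cohort is "closed to accrual once requisite enrollment is achieved: 200 total patients", while section 7.2.4 says "The accrual rate will be 5–6 patients / month over 2 years".

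**The concern.** The first power statement attaches both 99% and 80% to the same test, which cannot be right whatever method was used. The 80% may be a leftover design target, but the text does not say so.

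The 99% and the 78% also looked too high for a test of 92% against 97% or 96% with 200 men. Section 7.2.3 relies on 7.2.1 and 7.2.2 to justify enrolling 200, so these figures are the stated basis for the sample size on a primary objective. If they are wrong, readers underestimate the chance that an effective treatment fails the criterion.

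**Working it through.** **Inputs.** n = 200, null rate 92%, alternatives 97% and 96%, one-sided 5% (section 7.2.2); Wilson lower limit with Z = 1.645, success if L ≥ 0.92 (section 7.3.1.2). All 200 men are taken as evaluable at 2 years, because section 7.2 states no dropout allowance.

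**Step 1: can the stated figures be reproduced?** Normal-approximation powers for n = 200, one-sided 5%, p0 = 0.92:

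| Method | Power at 97% | Power at 96% |
|---|---|---|
| Stated in 7.2.2 | 99% (and 80%) | 78% |
| Score (null variance for the limit, alternative variance for power) | 93.7% | 72.9% |
| Null variance throughout | 83.2% | 67.0% |
| Wald, alternative variance | 99.4% | 89.3% |
| Arcsine | 93.8% | 77.9% |
| Logit, null variance | 99.0% | 88.1% |
| Logit, alternative variance | 80.2% | 65.3% |

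The Wald and null-variance logit formulas match the 99% but not the 78%. The arcsine formula matches the 78% but not the 99%. None gives both.

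**Step 2: the cut-off under the plan's rule.** With p = x/n,

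L = [(2np + Z²) − Z√(Z² + 4np(1 − p))] / [2(n + Z²)], where Z² = 2.706.

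- x = 190: L = (382.706 − 1.645 × 6.380) / 405.412 = 0.9181, which fails.
- x = 191: L = (384.706 − 1.645 × 6.090) / 405.412 = 0.9242, which passes.

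Success therefore requires at least 191 of 200.

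**Step 3: exact power, P(X ≥ c) for X ~ Binomial(200, p).**

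| Cut-off c | p = 0.92 (type I error) | p = 0.96 | p = 0.97 | p = 0.975 |
|---|---|---|---|---|
| 188 | 18.2% | 94.0% | 99.2% | 99.8% |
| 189 | 11.7% | 89.3% | 98.2% | 99.5% |
| 190 | 6.9% | 82.0% | 96.0% | 98.7% |
| **191** | **3.7%** | **71.9%** | **91.9%** | **97.0%** |
| 192 | 1.8% | 59.3% | 85.0% | 93.4% |

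The cut-off of 191 is also the most lenient one with exact type I error of 5% or less. The strictest cut-off that still gives 99% power at 97% is 188, with a type I error of 18.2% and 94.0% power at 96%. No cut-off yields the stated pair.

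**Step 4: what 99% would take.** With the cut-off at 191, power reaches 99% at a true rate of about 97.9%. At a true rate of 97% under the Wilson rule, no sample size below 296 reaches 99%. At 296 (cut-off 280) the exact type I error is 5.6%. Power is not monotone in n: it falls back to 98.7% at 310, and 99% is held throughout only from 326.

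**Step 5: sensitivity to evaluability** (illustrative assumption; the plan gives no rate).

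| Evaluable men | Cut-off | Power at 97% | Power at 96% | Type I error |
|---|---|---|---|---|
| 190 | 181 | 93.8% | 76.8% | 5.6% |
| 180 | 172 | 90.6% | 70.5% | 4.4% |
| 170 | 163 | 85.9% | 62.9% | 3.4% |

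**Separate check: accrual.** 5 × 24 = 120 and 6 × 24 = 144, against 200. Reaching 200 takes 200/6 = 33.3 to 200/5 = 40 months, or 200/24 = 8.3 men per month for two years.

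**The case against.** Five points can be made for the plan.

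- **The 78% is a recognisable approximation.** Section 7.2.2 names no power method, and the arcsine formula gives 77.9% at 96%. Part of the gap is discreteness: under the same Wilson rule exact power at 96% is 74.4% at n = 195, 69.9% at 204 and 79.9% at 205. This stands as a likely explanation of that one figure. It does not make 78% the power of the planned test at 200, and the same formula gives 93.8%, not 99%, at 97%.
- **One method comes close to both figures.** A two-sided 5% Wald formula with continuity correction gives 97.6% and 77.2%. It contradicts both the stated one-sided level and the Wilson rule.
- **97.5% may have been the intended alternative.** Power there is 97.0%, two points from 99%. But the sentence specifies 97%, and the 96% figure is still not met.
- **The consequence is small.** This stands. If 80% was the target at 97%, it is exceeded, and no decision changes.
- **The comparator is itself open to question.** The text says "an objective performance criteria (OPC) for low-risk patients treated with dose-escalated external beam RT is 92% 5-yr bDFS", yet elsewhere "we plan to accrue 200 eligible patients to compare the 2-year bDFS rate observed with SBRT to the 2-year OPC rate". Restated powers are therefore conditional on 92% as the null. That is a separate issue and does not alter the arithmetic here.

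**Conclusion.** The concern holds. Section 7.2.2 gives two powers for one test. Under the rule in 7.3.1.2 with 200 evaluable men, its 99% at a true rate of 97% should be 91.9% (7 points lower), and its 78% at 96% should be 71.9% (6 points lower). The probability of missing the criterion is about 8% and 28%, not 1% and 22%.

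The error lies in the reported operating characteristics, not in the decision rule. These figures rest on exact binomial calculation, a null of 92% and full evaluability at 2 years. The accrual mismatch is a timeline inconsistency and does not reduce power if accrual continues to 200.

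**What to change.** Replace the power statements in section 7.2.2 with wording such as:

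> With 200 men evaluable at 2 years and the rule in section 7.3.1.2 (at least 191 of 200 successes), exact power against 92% is about 92% if the true bDFS rate is 97% and about 72% if it is 96%. The exact type I error at 92% is 3.7%.

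Delete the reference to 80% power. State whether the planning rate is 97% or 97.5%; if 97.5%, the power is 97.0%. Say that the figures assume all 200 men are evaluable.

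Separately, in section 7.2.4 either lengthen the stated accrual period to about 33 to 40 months or raise the stated rate to about 8.3 men per month.

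The cost is wording only. Sample size, analysis and success criterion do not change. The plan will show somewhat less favourable power and, if the rate stays at 5 to 6 per month, a longer accrual period.

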## 7.3 STATISITCAL METHODS:

The *primary* objectives of this study are:

- To determine, in both low-risk and intermediate-risk cohorts, the rates of acute and late grade 3 or higher gastrointestinal and genitourinary toxicity observed during an initial 24 month follow up.
- To estimate the rate of biochemical Disease-Free Survival (bDFS), Phoenix and ASTRO definitions, at 2 years following hypofractionated SBRT for low and intermediate risk prostate cancer. Failure occurs when the PSA is  $\geq 2$  ng/ml more than the lowest PSA measurement before the current one, with no backdating.

The *secondary* objectives of this study are to:

- the rate of local failure: proportion of patients with local disease progression at 2 years

- rate of distant failure: proportion of patients with metastatic disease at 2 years
- rate of disease-free survival: median time from start of treatment until disease progression
- rate of disease-specific survival: death due to prostate cancer (excludes patients that relapse with inactive disease)
- overall survival: median length of time from either the date of diagnosis or the start of treatment for a disease, such as cancer, that patients diagnosed with the disease are still alive.
- quality of life (QOL) in generic and organ-specific domains using the FACT-G assessment tool

### 7.3.1 PRIMARY ENDPOINTS:

Wilson score interval is used to determine the confidence intervals for the expected proportion of patients experiencing a “success” outcome.

7.3.1.1 SAFETY: The upper limit of a one-sided 95% confidence interval for the expected proportion of patients experiencing any grade 3-5 acute or late toxicity as defined above in 7.1, is estimated by U, where

$$U = \frac{(2np + Z_{0.95}^2) + Z_{0.95} \sqrt{Z_{0.95}^2 + 4np(1-p)}}{2(n + Z_{0.95}^2)}$$

where:

p: the observed proportion of patients experiencing any grade 3-5 acute or late toxicity as defined above in 7.1;  
n: the total number of patients;  
 $Z_{0.95} = 1.645$ .

The intervention will be considered to be safe if this study’s result verifies that U is not above 10%i.

7.3.1.2 EFFICACY: The lower limit of a one-sided 95% confidence interval for the expected proportion of patients experiencing biochemical disease-free survival (bDFS) is estimated by L, where

$$L = \frac{(2np + Z_{0.95}^2) - Z_{0.95} \sqrt{Z_{0.95}^2 + 4np(1-p)}}{2(n + Z_{0.95}^2)}$$

where:

p: the observed proportion of patients experiencing bDFS;  
n: the total number of patients;  
 $Z_{0.95} = 1.645$ .

The SBRT intervention will be considered to be effective if this study’s result verifies that L is not below 92%.

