## 2.0 Objective

### PRIMARY OBJECTIVES:

- 2.1 The primary safety goal of this study is to determine, in both low-risk and intermediate-risk cohorts, the rates of acute and late grade 3-5 gastrointestinal and genitourinary toxicity observed during the initial 24 months following hypofractionated SBRT for prostate cancer. Patients will be followed for at least 5 years but possibly as long as 10 years, but initially we will strive to obtain 2 year follow-up results.
- 2.2 The primary efficacy goal is to document the rate of biochemical Disease-Free Survival (bDFS), Phoenix and ASTRO definitions, at 2 years. As above, we will ultimately aim for at least 5 years of follow-up but possibly as long as 10 years, with a short term goal of 2 years.

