#### 5.0 Treatment Administration and Evaluation

##### 5.1.1 EVALUATED STRUCTURES:

5.1.1.1 GTV: The Gross Tumor Volume (GTV) shall include the prostate; no more than 0.5cm of the immediately adjacent SV shall be included.

5.1.1.2 CTV: The Clinical Treatment Volume (CTV) shall include:

5.1.1.2.1 LOW-RISK PATIENTS: (CS T1b-T2a, PSA  $\leq$  10, Gleason score  $\leq$  6). Pathologic data from William Beaumont Hospital showed only 1% of low-risk patients had seminal vesicle (SV) involvement; this eliminates the need to treat SVs in this group. Thus the CTV shall equal the GTV.

5.1.1.2.2 INTERMEDIATE RISK PATIENTS: The Beaumont study also showed only 2% of “high-risk” patients (PSA  $>$  10, Gleason  $>$  6, and/or CS  $>$  T2a) had SV involvement distal to 2 cm from the prostate. The intermediate risk group CTV shall therefore be the GTV plus the proximal 2cm of SVs.

5.1.1.3 PTV: The prescription dose shall be delivered to the Planning Tumor Volume (PTV). While the static targeting accuracy of the radiosurgery machines are about 1mm^69, deformation of the prostate, and target movement occurring after imaging but before dose delivery could contribute to targeting uncertainty. Although the cumulative targeting uncertainty has not been accurately quantified, the 3-5mm GTV to PTV expansion employed in the Stanford series appears more than adequate. Stanford phase I data showed safely and early clinical response rates are acceptable with this PTV. Thus the PTV shall equal the CTV expanded 3mm posteriorly, and 5mm in all other dimension.

5.1.1.4 Microscopic evaluation of prostatectomy specimens may demonstrate EXTRACAPSULAR EXTENSION: 99% of microscopic extra prostatic disease should be within 3- 5mm of the prostate. Since 7.25Gy is prescribed 3-5mm outside the prostate, a dose adequate to address microscopic disease ( $\geq$ 6Gy x 5) will easily be delivered at 5mm.

5.1.1.5 NORMAL TISSUES: CONTOURING REQUIRED: The structures listed below will be contoured and evaluated with DVH analysis. Bowel peristalsis and bladder filling change the size and location of normal structures. If the CT and MRI (or secondary CT) show normal tissues in different locations immediately adjacent (i.e., within  $<$  2cm) the prostate, the contoured structure shall be a larger composite of both image sets. Grid size should be sufficiently large to include the entire structure.

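### The primary safety objective is set for both risk cohorts, but section 7.3.1.1 plans only one pooled toxicity rate and limit, so the objective is not answered as stated

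*Combined protocol and SAP*

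**What the plan says.** The Protocol Summary, section 2.1 and section 7.3 all state the primary safety objective by cohort. Section 2.1 asks for "in both low-risk and intermediate-risk cohorts, the rates of acute and late grade 3-5 gastrointestinal and genitourinary toxicity" over the first 24 months. Section 7.3, which opens the statistical methods, repeats it: "To determine, in both low-risk and intermediate-risk cohorts, the rates of acute and late grade 3 or higher gastrointestinal and genitourinary toxicity".

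Section 7.3.1.1 is the only safety analysis of the primary endpoint. It defines "p: the observed proportion of patients experiencing any grade 3-5 acute or late toxicity as defined above in 7.1" and "n: the total number of patients". The intervention is safe if the result "verifies that U is not above 10" percent. There is one p, one n and one verdict.

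The related sections are pooled as well. Section 7.2.1 powers a single rate on 200 patients. Section 7.2.3 has a heading that promises relative enrollment but gives only a total: "The test cohort will be closed to accrual once requisite enrollment is achieved: 200 total patients". Section 7.4 applies its stopping rule to all participants together and tabulates toxicity by category and grade.

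The cohorts do not have the same target. For low-risk men the CTV equals the GTV. For the others, section 5.1.1.2.2 says "The intermediate risk group CTV shall therefore be the GTV plus the proximal 2cm of SVs", and the PTV is expanded from the CTV.

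**The concern.** An objective to determine rates in two cohorts needs an estimate in each, and the plan produces neither. An analyst who followed section 7.3.1.1 to the letter would report one number for the mixture.

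This matters because the target volume differs by risk group, which is a reason in the design not to assume equal rates. A pooled proportion is a weighted average, and the weights are whatever split happens to enroll. If low-risk men predominate and have few events, a pooled result under the limit says little about intermediate-risk men, yet the verdict is worded for the intervention as a whole.

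**Working it through.** **Inputs from the documents.** n = 200 (7.2.1, 7.2.3); limit 10%, z = 1.645 and the Wilson formula (7.3.1.1); 20% as the rate at which toxicity counts as excessive (7.2.1).

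**Assumptions, because the documents give no value.** Intermediate-risk numbers from 40 to 100 of 200; true low-risk rates from 0% to 5%. The only mix quoted in section 7.2 is 75% low-risk and 25% intermediate-risk in a cited HDR series, which would correspond to 150/50 here.

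**Step 1. The plan's own power figure.** For 20% against 10%, n = 200, one-sided 5%, the normal approximation is Φ[(0.10√200 − 1.645 × 0.30)/0.40] = 98.9%. An exact binomial test that rejects at 28 or more of 200 has alpha 4.3% and power 98.9%. The stated 99% is reproduced. It applies to a pooled rate of 20%.

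**Step 2. Largest count that passes.** U = [(2np + z²) + z√(z² + 4np(1−p))] / [2(n + z²)], with z² = 2.706.
- 13/200: (28.706 + 1.645 × √51.326)/405.412 = (28.706 + 11.785)/405.412 = 9.99%, a pass.
- 14/200: U = 10.58%, a fail.

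So the pooled rule allows at most 13 patients with toxicity (6.5%).

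**Step 3. Observed patterns that pass.** A 20% intermediate-risk rate in m men is 0.20m events. This fits within 13 only if m ≤ 13/0.20 = 65, or 32.5% of 200.
- m = 40: 8/40 plus 5/160 (3.1%) = 13/200, passes.
- m = 50: 10/50 plus 3/150 (2.0%) = 13/200, passes. The cohorts' own limits are 30.7% [(22.706 + 9.691)/105.412] and 4.9%.
- m = 60: 12/60 plus 1/140 (0.7%) = 13/200, passes.
- m = 80 or 100: 16 or 20 events already exceed 13, so the trial fails.

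**Step 4. Probability of a safe verdict at a true intermediate-risk rate of 20%.** P(X + Y ≤ 13), with X ~ Bin(m, 0.20) and Y ~ Bin(200 − m, low-risk rate), by exact convolution:

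| Intermediate-risk men | Low-risk 0% | 2% | 3% | 5% |
|---|---|---|---|---|
| 40 | 98% | 78% | 60% | 26% |
| 50 | 89% | 57% | 40% | 15% |
| 60 | 69% | 37% | 24% | 8% |
| 80 | 25% | 10% | 6% | 1.9% |
| 100 | 4.7% | 1.8% | 1.1% | 0.4% |

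**Step 5. Would section 7.4 catch it?** Accrual stops at an observed pooled rate of about one third or more. A pooled rate near 6.5% is far below that, so the rule would not be expected to act.

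**Step 6. What cohort limits would look like.** In a cohort of 50, 1/50 gives U = 8.5% and 2/50 gives U = 11.4%.

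**The case against.** The pooled test is coherent in itself. Section 7.2 tests one rate, sizes the trial for it and speaks of one test cohort; section 7.3.1.1 makes a claim about the intervention. On that reading the mention of both cohorts describes who is enrolled. This stands as a defense of the decision rule. It does not supply the cohort rates that three statements of the objective call for.

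A reader might infer that the plan will pass SBRT as safe while intermediate-risk toxicity is twice the limit. The documents do not support that as an unconditional statement. It needs at most 65 intermediate-risk men and few low-risk events, and the documents fix neither. At an even split the pooled rule protects well: the probability is at most 4.7%, even with no low-risk toxicity. The result is also sensitive to the low-risk rate. The background section gives 2 of 41 men (about 5%) with grade 3 late urinary toxicity in the series at this prescription dose, with no risk mix stated there, and 1 grade 3 event among 40 low-risk men (2.5%) at a lower dose.

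A reader might also infer that the larger target means more toxicity. The documents do not show this. The rectal and bladder constraints in 5.1.2.3 and 5.1.2.4 are the same for both groups.

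Nor would a concentration of events necessarily stay hidden. Section 7.4 has every grade 3 or higher event described patient by patient with relevant baseline data, and risk group follows from baseline stage, Gleason score and PSA. With at most 13 such patients in a passing trial, an imbalance could be noticed. That softens the concern, but a listing is not a planned rate with an interval.

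Finally, requiring each cohort to meet the 10% limit would be badly underpowered. A cohort of 50 passes only with 0 or 1 events, which happens 56% of the time at a true 3% and 28% at 5%. This objection stands, and no such requirement is proposed here.

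**Conclusion.** The point holds as a gap between objective and analysis. The primary safety objective names two cohorts, the planned analysis gives one pooled proportion and limit, and nothing elsewhere in the plan fills the gap. This part rests on the text alone.

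The size of the consequence rests on assumptions. With 50 intermediate-risk men at a true 20%, the pooled rule returns a safe verdict 57% of the time if the low-risk rate is 2% and 15% if it is 5%. With 100 such men the figures are 1.8% and 0.4%. The calculation takes all 200 patients as evaluable and outcomes as independent. Because the split is not fixed, how well the pooled rule protects intermediate-risk men depends on who enrolls. The pooled test remains valid for the enrolled mixture, and its stated power is correct for that purpose.

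**What to change.** In section 7.3.1.1:

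1. Keep the pooled U as the decision rule, with the sample size unchanged.
2. Add, for each risk cohort as defined in section 4.3, the number of patients, the observed proportion with grade 3-5 GI/GU toxicity, and the same one-sided 95% Wilson upper limit, reported beside the pooled result.
3. State that a pooled safe verdict applies to the enrolled mix of risk groups and is not a claim for either cohort alone.

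The cost is two extra intervals from data already collected and one sentence on scope. The drawback is imprecision: in a cohort of 50 a single event moves U from 8.5% to 11.4%, so the cohort results should be labeled as estimates and not as powered tests.
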